3.3 Safety Endpoint(s)

The safety parameters include including adverse event (AE) monitoring, vital sign measurements, electrocardiogram (ECG) variables, clinical laboratory testing (hematology, chemistry, and urinalysis), and Columbia Suicide Severity Rating Scale (C-SSRS). For clinical laboratory, vital sign, and ECG parameters, the last non-missing safety assessment before the first dose of treatment will be used as the baseline for all analyses of that safety parameter.

All AEs and other safety data will be presented in the listings at the subject level.

4.0 Analysis Populations

The modified intent-to-treat 1 (mITT1) population includes all enrolled subjects who received at least 1 dose of study drug, have a baseline assessment, and have at least 1 postbaseline assessment during the open-label atogepant treatment period. The modified intent-to-treat 2 (mITT2) population includes all enrolled subjects who received at least 1 dose of study drug, have a baseline assessment, and have at least 1 postbaseline assessment during the open-label atogepant + ubrogepant treatment period. The mITT1 or mITT2 populations will be used for all efficacy analyses.

The Safety Population 1 consists of all subjects who received at least 1 dose of study drug during the open-label atogepant treatment period. The Safety Population 2 consists of all subjects who received at least 1 dose of study drug during the open-label atogepant + ubrogepant treatment period. The Safety Population 1 or Safety Population 2 will be used for safety analyses.

5.0 Subject Disposition

Summaries will be provided for subjects in each of the following categories:

- Subjects who were screened;
- Subjects enrolled in the study;
- Subjects who completed the study (or did not with associated reasons);
- Subjects who discontinued the study drug, including atogepant and ubrogepant;
- Subjects who took at least one dose of study drug during the open-label atogepant treatment period (Safety Population 1);
- Subjects who completed open-label atogepant treatment period;
- Subjects who took at least one dose of study drug, either atogepant or ubrogepant, during the open-label atogepant + ubrogepant treatment period (Safety Population 2);
- Subjects who completed open-label atogepant + ubrogepant treatment period;
- Subjects who prematurely discontinued the open-label atogepant treatment period (including reasons for premature discontinuation);
- Subjects who prematurely discontinued the open-label atogepant + ubrogepant treatment period (including reasons for premature discontinuation);
- Subjects who prematurely discontinued the study (including reasons for premature discontinuation);
- Subjects in the mITT 1 Population;
- Subjects in the mITT 2 Population.

Screen failure subjects (i.e., subjects who consented to participate in the study but were not enrolled) and the associated reasons for failure to enroll will be summarized and listed for all screened subjects.

The summary of subject accountability by investigator also will include the number of subjects who enrolled in the study, completed the study, discontinued study drug, and

subjects in the mITT 1, mITT 2, Safety Population 1, and Safety Population 2, respectively.

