APPENDIX D. ACTIVITY SCHEDULE

The following table shows the required activities. The individual activities are described in detail in the Operations Manual ([Appendix F](#)).

Study Activities Table

Activity	Visit 1 Screening	Visit 2 Baseline	Visit 3	Visit 4	Visit 5	Visit 6	Visit 7	Visit 8 OR Early Termination	Visit 9 Safety Follow-Up Visit
	Week -1	Day 1 +3days	Week 4 ±3days	Week 8 ±3days	Week 12 ±3days	Week 16 ±3days	Week 20 ±3days	Week 24 +3days	Week 28 ±3days
❑ INTERVIEWS & QUESTIONNAIRES									
Informed consent	✓								
Eligibility criteria	✓	✓							
Medical/surgical history	✓								
Migraine history	✓								
Adverse event assessment	✓	✓	✓	✓	✓	✓	✓	✓	✓
Prior/concomitant therapy	✓	✓	✓	✓	✓	✓	✓	✓	✓
Patient-reported outcomes: HIT-6		✓	✓	✓	✓	✓	✓	✓	
Patient-reported outcomes: MSQ v2.1	✓	✓	✓	✓	✓	✓	✓	✓	
Patient-reported outcomes: WPAI:MIGRAINE		✓	✓	✓	✓	✓	✓	✓	
Patient-reported outcomes: PGIC (atogepant)					✓				
Patient-reported outcomes: PGIC (atogepant + ubrogepant)								✓	
Patient-reported outcomes: PHQ-4		✓	✓	✓	✓	✓	✓	✓	
Patient-reported outcomes: MTOQ-6						✓	✓	✓	
Patient-reported outcomes: Subject satisfaction with atogepant					✓			✓	
Patient-reported outcomes: subject satisfaction with ubrogepant								✓	

	Visit 1 Screening	Visit 2 Baseline	Visit 3	Visit 4	Visit 5	Visit 6	Visit 7	Visit 8 OR Early Termination	Visit 9 Safety Follow-Up Visit
Activity	Week -1	Day 1 +3days	Week 4 ±3days	Week 8 ±3days	Week 12 ±3days	Week 16 ±3days	Week 20 ±3days	Week 24 +3days	Week 28 +3days
Patient-reported outcomes: subject satisfaction with atogepant & ubrogepant								✓	
Investigator interviewer questionnaire migraine - screening	✓								
Investigator interviewer questionnaire migraine - Visit 2-5		✓	✓	✓	✓				
Investigator interviewer questionnaire migraine - Visit 6-8						✓	✓	✓	
C-SSRS	✓	✓	✓	✓	✓	✓	✓	✓	✓
LABORATORY & SITE EXAMINATIONS									
12-lead ECG	✓				✓			✓	
Height (screening only) and weight	✓	✓	✓	✓	✓	✓	✓	✓	✓
Vital signs	✓	✓	✓	✓	✓	✓	✓	✓	✓
Physical examination	✓							✓	✓
Urine pregnancy test	✓	✓	✓	✓	✓	✓	✓	✓	✓
CENTRAL LABORATORY									
Clinical laboratory tests	✓	✓	✓	✓	✓	✓	✓	✓	✓
PK (optional): predose at Visit 2		✓		✓				✓	
Biomarker samples (optional): predose at Visit 2		✓		✓				✓	✓
Pharmacogenetic sample – blood (optional)	✓								
Rx TREATMENT									
IRT entry	✓	✓	✓	✓	✓	✓	✓	✓	
Dispense study drug (atogepant)		✓	✓	✓	✓	✓	✓		
Dispense study drug (ubrogepant)					✓	✓	✓		
Perform drug reconciliation			✓	✓	✓	✓	✓	✓	

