2.0 Study Design and Objectives

2.1 Objectives, Hypotheses and Estimands

The primary objective of this study is to evaluate the safety and tolerability of the concomitant use of ubrogepant 100 mg for the acute treatment of breakthrough migraine headache in subjects taking atogepant 60 mg once daily for preventive treatment of EM.

The exploratory objectives are:

- To evaluate the clinical benefit of the concomitant use of ubrogepant 100 mg, taken as needed, and atogepant 60 mg once daily in subjects with EM.
- To explore the efficacy of ubrogepant 100 mg, taken as needed, for the acute treatment of migraine in subjects taking atogepant 60 mg once daily for preventive treatment of EM.

The efficacy endpoints are exploratory in this study; therefore, no estimand attributes for efficacy endpoints will be provided.

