10.2.1 Treatment-Emergent Adverse Events

Treatment-emergent AEs are defined as any AE with the onset that is after the first dose of study drug. Events when the onset date is the same as the study drug start date are assumed to be treatment-emergent. An AE that occurs more than 30 days after the last dose of open-label study treatment or Visit 8 whichever comes later will not be counted as a TEAE.

The number and percentage of subjects experiencing treatment-emergent AEs will be summarized by the open-label atogepant treatment period, the open-label concomitant atogepant + ubrogepant treatment period, and the entire treatment period.

TEAEs that started after the date of last dose of study treatment will be considered as newly emergent. The number and percentage of subjects reporting newly emergent TEAEs will be summarized by system organ class and preferred term.

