10.3 Laboratory Data

Data collected from central laboratories, including additional laboratory testing due to an SAE, will be used in all analyses, except for Baseline where SAE-related laboratory assessments on or before the first dose of study drug without timestamp will be excluded. The details for SAE-related laboratory baseline can be found in the SPP. The clinical laboratory tests defined in the protocol (e.g., hematology, clinical chemistry and urinalysis) will be summarized.

Each laboratory variable will be summarized for all time points (starting with Baseline) with the number of non-missing observations, mean and standard deviation, median, Q1, Q3, minimum and maximum. Mean change from baseline to each applicable post-baseline visit will be summarized with the number of observations, baseline mean, and visit mean. The change from baseline mean, standard deviation, median, Q1, Q3, minimum and maximum will be presented for the mean change from baseline. In addition, descriptive statistics for values and changes from the baseline values in conventional units at each assessment time point will be presented for selected clinical laboratory parameters listed in Appendix D. A description of reporting the lab values in conventional units in patient narratives (along with the standard reporting in SI units) is presented at the end of Appendix D.

Changes in laboratory parameters will be summarized using shift tables categorized as low, normal, or high based on the normal ranges of the laboratory used for each sample. A shift table will be provided to summarize shifts from baseline to the final post-baseline value for all lab categories.

Laboratory abnormalities will be evaluated based on potentially clinically significant (PCS) criteria (Table 4). For each laboratory PCS criterion, the number and percentage of subjects who have a laboratory value meeting the criteria will be summarized in Safety Populations 1 and 2 for each treatment period and overall. Listings will be provided to summarize subject-level laboratory data for subjects meeting PCS criteria.

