The number and percentage of subjects meeting each of the criteria for postbaseline hepatic laboratory abnormalities listed in Table 5 will be summarized. The percentages will be calculated relative to the number of subjects with at least 1 available postbaseline assessment. The numerator will be the total number of subjects having at least 1 postbaseline value that meets the specific category during the study. A supportive listing will also be provided.

The number and percentage of subjects with an adjudicated case (i.e., ALT \geq 3 x ULN and/or AST \geq 3 x ULN) will be summarized by relationship of ALT or AST elevation to study medication. The percentages will be calculated relative to the number of subjects with at least 1 adjudicated case. The numerator will be the number of subjects with at least 1 adjudicated case in the specific category of relationship. If a subject has more than 1 adjudicated case, he or she will be counted in the most relevant category of relationship.

Subjects with an adjudicated case (i.e., ALT \geq 3 x ULN or AST \geq 3 x ULN) will be listed with their ALT and AST assessments, adjudication dates, relationship of ALT or AST elevation to study medication, and confounding factor(s). Additional listings will be provided for subjects who meet ALT \geq 3 x ULN or AST \geq 3 x ULN and/or potential Hy's law and have one of the following categories: at least 1 abnormal liver biochemistry risk factor, at least 1 liver disease sign and symptom, at least 1 liver diagnostic test performed, consultation with a specialist for liver evaluation, liver lab tests performed, and drug screen performed, respectively.

Potential Hy's Law criteria within a 24-hour window is defined by a postbaseline evaluation of alanine aminotransferase (ALT) or aspartate aminotransferase (AST) \geq 3 x ULN, along with total bilirubin (TBL) \geq 2 x ULN and a non-elevated alkaline

phosphatase (ALP) < 2 x ULN, all based on blood draws collected within a 24-hour period. Patients who meet the potential Hy's Law criteria will be summarized. Supportive listing will also be provided.

A listing of urine pregnancy test results will be provided for female subjects of child-bearing potential with at least one positive result.

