10.6 Safety Subgroup Analyses

Two subgroups will be applied in subgroup analyses based on subjects' ubrogepant use:

Subgroup by number of ubrogepant use days:

- Never used ubrogepant
- Low ubrogepant use: 1-3 days of ubrogepant taken in the atogepant + ubrogepant treatment period
- Moderate ubrogepant use: 4-9 days of ubrogepant taken in the atogepant + ubrogepant treatment period
- High ubrogepant use: ≥ 10 days of ubrogepant taken in the atogepant + ubrogepant treatment period

Subgroup by number of ubrogepant doses taken:

- Never used ubrogepant
- Low ubrogepant use: 1-6 doses of ubrogepant taken in the atogepant + ubrogepant treatment period
- Moderate ubrogepant use: 7-18 doses of ubrogepant taken in the atogepant + ubrogepant treatment period
- High ubrogepant use: 19+ doses of ubrogepant taken in the atogepant + ubrogepant treatment period

TEAE, serious TEAE, and TEAE leading to study drug discontinuation will be summarized by subgroups.

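### Table 5 hepatic and ECG PCS counts pool the atogepant-only period with concomitant use, and the non-AE safety summaries never isolate subjects who took ubrogepant

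*SAP*

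**What the plan says.** SAP 2.1 sets the primary objective: to "evaluate the safety and tolerability of the concomitant use of ubrogepant 100 mg" in subjects on daily atogepant. SAP 4.0 states that "The Safety Population 2 consists of all subjects who received at least 1 dose of study drug" in the concomitant period, and SAP 5.0 makes clear that either drug qualifies: subjects who "took at least one dose of study drug, either atogepant or ubrogepant, during the open-label atogepant + ubrogepant treatment period (Safety Population 2"). Ubrogepant is as needed (SAP 6.0), so zero doses is possible, and SAP 10.6 provides a never-used level. Under 10.6, "TEAE, serious TEAE, and TEAE leading to study drug discontinuation will be summarized by subgroups"; no other safety summary is split by use.

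The counting windows differ. Laboratory PCS counts (Table 4) "will be summarized in Safety Populations 1 and 2 for each treatment period and overall". The hepatic counts (Table 5 of SAP Appendix C) take subjects "having at least 1 postbaseline value that meets the specific category during the study". The ECG PCS numerator in SAP 10.5.1 has the same whole-study window. The vital-sign PCS count in SAP 10.4 names no window. The safety baseline precedes the first dose of study drug (SAP 10.1), which is atogepant on Day 1. In Protocol Appendix D the row "Dispense study drug (ubrogepant") is first ticked at Visit 5.

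**The concern.** Two features separate the tables from the question they should answer.

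First, a Table 5 or ECG PCS finding that arose on atogepant alone enters the same count as one that arose after ubrogepant became available. The count cannot say which regimen the finding belongs to.

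Second, for every safety domain other than AEs, no planned summary is restricted to subjects exposed to both drugs. If never-users have a different event risk from users, second-period rates misstate the risk of concomitant use, and for findings not reported as AEs only subject-level listings would show it.

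Both features bear on the primary objective. No hypothesis test, alpha or power is involved; attribution and description are at stake.

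**Working it through.** **1. The plan's own figures.** SAP 2.4 gives 235 subjects, 15% dropout in the first period, about 200 entering the second, and a 95% CI half-width of about 3% to 5%. Check: 235 × 0.85 = 199.75. With half-width = 1.96 × √(p(1−p)/n) and n = 200, an assumed p of 5%, 10% or 15% gives 3.02, 4.16 or 4.95 points. The stated figures reproduce.

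**2. Window and split, side by side.**

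| Summary | Window | Split by ubrogepant use |
|---|---|---|
| TEAEs (SAP 10.2, 10.6) | each period and overall | yes, for three TEAE categories |
| Laboratory PCS, Table 4 (10.3) | each period and overall | no |
| Hepatic, Table 5 (10.3) | whole study | no |
| Vital-sign PCS, Table 6 (10.4) | not stated | no |
| ECG PCS, Table 7 (10.5.1) | whole study | no |
| C-SSRS (10.5.2) | by period, overall and follow-up | no |
| Laboratory, vital-sign and ECG descriptive statistics | by timepoint | no |

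**3. Schedule (Protocol Appendix D).** ECGs are at Visits 1, 5 and 8, so 1 of 2 post-baseline ECGs is at the visit where ubrogepant is first dispensed. Laboratory tests and vital signs are at Visits 1 to 9. Post-baseline visits are 3 to 9, seven in all; Visits 3, 4 and 5 fall no later than dispensing: 3/7 = 43%.

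**4. Which Table 5 rows are affected.** Rows: 5 parameters × 7 cut-offs + 2 concurrent elevations + 1 potential Hy's law = 38. Four (ALT ≥ 3, AST ≥ 3, ALP ≥ 3 and total bilirubin ≥ 1.5 × ULN) also get a by-period count through Table 4, which leaves 34. Most of these are nested cut-offs of the same parameters, so 34 is not a count of separate gaps. The concurrent-elevation and potential Hy's law rows are among those shown only pooled.

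**5. Size of the pooling effect.** Assume the same risk q at each scheduled assessment. If the same subjects are abnormal throughout, whole-study and second-period counts are equal (ratio 1.0). If assessments are independent:
- ECG: [1−(1−q)²]/q. At q = 1%, 1.99%/1.00% = 1.99.
- Hepatic at q = 1%, by handling of Visit 9:
  - In the second period: [1−0.99⁷]/[1−0.99⁴] = 6.79%/3.94% = 1.72.
  - In the study total only: [1−0.99⁷]/[1−0.99³] = 6.79%/2.97% = 2.29.
  - In neither: [1−0.99⁶]/[1−0.99³] = 5.85%/2.97% = 1.97.

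The hepatic figure changes with a choice the SAP does not state, so no single upper ratio should be quoted.

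**6. Dilution by never-users.** Let u be the never-user share of Safety Population 2 (not given) and r the never-user risk divided by the ever-user risk. Reported rate = ever-user rate × [1 − u(1−r)]. For an ever-user rate of 10% and u = 10% (both assumed): 9.0% at r = 0, 9.5% at r = 0.5, 10.0% at r = 1 and 10.5% at r = 1.5. For r below 1, the relative understatement is at most u, that is 5%, 10% or 20% for an assumed u of 5%, 10% or 20%.

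**7. Precision in an ever-user set.** At a 10% event rate the half-width is 4.16 points at n = 200, 4.27 at 190, 4.38 at 180 and 4.65 at 160. Exact 95% CIs: 20/200 gives 6.22% to 15.02%; 18/180 gives 6.04% to 15.34%.

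**The case against.** The case for leaving the plan as it is has substance.

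- **The hepatic safeguards are considerable.** A reader might infer that all hepatic PCS counts pool the two periods. They do not: the hepatic PCS criteria sit in Table 4, which is reported by period. ALT or AST ≥ 3 × ULN is an adverse event of special interest entered on the AE form (Protocol 6.1, SAP 10.2.5). Each such case is adjudicated for relationship to study drug (Protocol 5.10) and listed with its assessments and confounders (SAP 10.3). Potential Hy's law cases meet the same enzyme threshold and fall within that review.
- **Dates can be recovered.** Laboratory, vital-sign and ECG statistics are given by timepoint and PCS cases are listed. With two scheduled post-baseline ECGs, dating an ECG finding is easy.
- **Safety Population 2 is defensible.** The regimen is as-needed ubrogepant on daily atogepant, and the set matches Protocol 7.2. Protocol 5.4 directs ubrogepant to all breakthrough attacks in this period, so an adherent never-user had no attack to treat. An ever-user set is selected on behaviour after Visit 5.
- **The likely dilution is small** beside a half-width of about 4 points, and 10.6 already separates never-users for TEAEs.

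These points limit the concern without removing it. Listings and adjudication let a reader rebuild individual cases, but they do not give a second-period count for concurrent elevations, potential Hy's law or ECG PCS. Nor do they show any non-AE summary in subjects exposed to both drugs.

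A reader might also infer from "Treatment-emergent AEs are defined as any AE with the onset that is after the first dose of study drug" that the never-used row in 10.6 would be filled by the roughly 35 subjects (235 − 200) expected to stop before ubrogepant is offered. The use bands in 10.6 are defined by intake in the concomitant period, and 10.2.1 summarizes TEAEs by period, so Safety Population 2 is the natural reading. The missing population and period label there is only a detail to fill in.

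**Conclusion.** The point holds in limited form and is worth acting on because it touches the sole primary objective and uses data already collected. The counts shown only pooled are ECG PCS and the Table 5 rows without a Table 4 counterpart, including concurrent elevations and potential Hy's law; vital-sign PCS has no stated window. Separately, laboratory, hepatic, vital-sign, ECG and C-SSRS summaries offer no view of ubrogepant users.

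The schedule fractions (1 of 2 and 3 of 7) come directly from Protocol Appendix D. The ECG ratio of 1.0 to about 2.0 rests on assumed equal per-assessment risk and on the degree of persistence. The hepatic ratio also depends on the handling of Visit 9.

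The documents do not support a claim that second-period rates are biased downward. Neither the never-user share nor the event rates are given: the rate is understated if never-users have lower risk, overstated if they have higher risk, and unaffected if the risks are equal.

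**What to change.** Change the SAP only.

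1. Report Table 5 hepatic, ECG PCS and vital-sign PCS counts by period. Assign Visit 5 values to the atogepant-only period. Show Visit 9 as follow-up, or assign it explicitly.
2. Keep Safety Population 2 and add a supplementary set of subjects with at least one ubrogepant dose. Repeat the second-period TEAE, laboratory PCS, hepatic, vital-sign PCS, ECG and C-SSRS summaries in it.
3. Give exact 95% CIs for TEAE incidence. SAP 2.4 justifies the sample size by interval width, while SAP 10.1 plans only numbers and percentages.
4. Name the population and period in 10.6 (one line).
5. Record the added set in Appendix F, which now reports no changes from the protocol.

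The cost is a few more tables from existing shells. Dosing is recorded (Protocol 5.7) and ubrogepant doses and days are already summarized (SAP 6.0); the Protocol 7.2 sets stand. The downsides are a slightly smaller denominator and a set selected on use after Visit 5, which is why it should supplement Safety Population 2 and not replace it.

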6.0 Study Treatment Duration and Compliance

Duration of treatment for atogepant, defined for each subject as last dose date minus first dose date + 1, will be summarized for the Safety Population 1 and Safety Population 2.

Duration of treatment for atogepant will be summarized for each period (open-label atogepant period or open-label atogepant + ubrogepant period) and the entire open-label period using the number of subjects treated, mean, standard deviation, median, minimum and maximum. In addition, the number and percentage of subjects in each treatment duration of ≥ 1 day, ≥ 7 days, ≥ 14 days, ≥ 21 days, ≥ 28 days, ≥ 35 days, ≥ 42 days, ≥ 49 days, ≥ 56 days, ≥ 63 days, ≥ 70 days, ≥ 77 days, ≥ 84 days, ≥ 91 days, ≥ 98 days, ≥ 105 days, ≥ 112 days, ≥ 119 days, ≥ 126 days, ≥ 133 days, ≥ 140 days, ≥ 147 days, ≥ 154 days, ≥ 161 days, ≥ 168 days will be summarized.

Duration of treatment for ubrogepant, defined as the number of doses and days of ubrogepant taken, will be summarized for the Safety Population 2, by the number of subjects treated, mean, standard deviation, median, minimum and maximum.

Treatment compliance of atogepant for a specific period (open-label atogepant period and open-label atogepant + ubrogepant period) is defined as the number of atogepant doses actually taken by a subject during that period divided by the number of atogepant doses that were expected to be taken during the same period multiplied by 100. Percent treatment compliance will be summarized in each period for the Safety Population 1 and Safety Population 2.

Ubrogepant is taken as needed, so no treatment compliance will be provided for ubrogepant.

7.0 Demographics, Baseline Characteristics, Medical History, and Prior/Concomitant Medications

7.1 Demographics and Baseline Characteristics

Demographics and baseline characteristics will be summarized for the Safety Population 1 and 2. Continuous demographic variables include age, weight, height, and body mass index (BMI). Categorical demographic variables include sex, ethnicity (Hispanic or Latino, Not Hispanic or Latino), race, race group (White, All Other Races), BMI group (< 25, 25-30, and \geq 30), and age group (< 20, 20-29, 30-39, 40-49, 50-59, 60-69, and \geq 70).

Disease characteristics are contained in migraine history, including diagnosis, duration of disorder, migraine prevention medication in the past, average number of migraine and headache days per month at baseline and in the last 3 months, and acute medications taken to treat migraine headaches.

Categorical variables will be summarized with the number and percentage of subjects; percentage will be calculated based on the non-missing observations. Continuous variables will be summarized with descriptive statistics (number of non-missing observations, mean and standard deviation, median, Q1, Q3, minimum, and maximum).

